#### **Attribution of Toxicity:**

When study interventions are administered in combination, attribution of an adverse event to a single component is likely to be difficult. Therefore, while the investigator may attribute a toxicity event to pembrolizumab monotherapy, coformulations, or IO combinations, pembrolizumab monotherapy, coformulations, or IO combinations must be held according to the criteria in the Dose Modification and Toxicity Management Guidelines for Immune-Related Adverse Events.

In these cases where the toxicity is attributed to pembrolizumab coformulations or IO combinations, re-initiation of pembrolizumab as a monotherapy may be considered after communication with and agreement by the Sponsor.

**Holding Study Interventions:**

When study interventions are administered in combination and if the AE is considered immune-related, pembrolizumab monotherapy, coformulations, or IO combinations should be held according to recommended Dose Modification criteria.

If the toxicity does not resolve or the criteria for resuming treatment are not met, the participant must be discontinued from pembrolizumab monotherapy, coformulations, or IO combinations.

**Restarting Study Interventions:**

Participants may restart pembrolizumab monotherapy, coformulations, or IO combinations as described below:

If the toxicities do resolve and conditions are aligned with what is defined in the Dose Modification and Toxicity Management Guidelines for irAEs, pembrolizumab monotherapy, coformulations, or IO combinations may be restarted at the discretion of the investigator.

Dose Modification and Toxicity Management Guidelines for irAEs associated with pembrolizumab monotherapy, coformulations, or IO combinations are provided in [Table 5](#).

**Table 5 Dose Modification and Toxicity Management Guidelines for Immune-related Adverse Events Associated with Pembrolizumab Monotherapy, Coformulations or IO Combinations**

General instructions:				
irAEs	Toxicity Grade (CTCAEv4.0)	Action With Pembrolizumab Monotherapy, Coformulations or IO Combinations	Corticosteroid and/or Other Therapies	Monitoring and Follow-up
Pneumonitis	Grade 2	Withhold	
 
Administer corticosteroids (initial dose of 1-2 mg/kg prednisone or equivalent) followed by taper
 
	
 
Monitor participants for signs and symptoms of pneumonitis
 
Evaluate participants with suspected pneumonitis with radiographic imaging and initiate corticosteroid treatment
 
Add prophylactic antibiotics for opportunistic infections
 

	Recurrent Grade 2 or Grade 3 or 4	Permanently discontinue		
Diarrhea / Colitis	Grade 2 or 3	Withhold	
 
Administer corticosteroids (initial dose of 1-2 mg/kg prednisone or equivalent) followed by taper
 
	
 
Monitor participants for signs and symptoms of enterocolitis (ie, diarrhea, abdominal pain, blood or mucus in stool with or without fever) and of bowel perforation (ie, peritoneal signs and ileus)
 
Participants with <math>\ge</math>Grade 2 diarrhea suspecting colitis should consider GI consultation and performing endoscopy to rule out colitis
 
Participants with diarrhea/colitis should be advised to drink liberal quantities of clear fluids. If sufficient oral fluid intake is not feasible, fluid and electrolytes should be substituted via IV infusion.
 

	Recurrent Grade 3 or Grade 4	Permanently discontinue		

irAEs	Toxicity Grade (CTCAEv4.0)	Action With Pembrolizumab Monotherapy, Coformulations or IO Combinations	Corticosteroid and/or Other Therapies	Monitoring and Follow-up
AST / ALT Elevation or Increased Bilirubin	Grade 2	Withhold	
 
Administer corticosteroids (initial dose of 0.5-1 mg/kg prednisone or equivalent) followed by taper
 
	
 
Monitor with liver function tests (consider weekly or more frequently until liver enzyme value returned to baseline or is stable)
 

	Grade 3 or 4	Permanently discontinue	
 
Administer corticosteroids (initial dose of 1-2 mg/kg prednisone or equivalent) followed by taper
 
	
T1DM or Hyperglycemia	New onset T1DM or Grade 3 or 4 hyperglycemia associated with evidence of $\beta$ -cell failure	Withhold a	
 
Initiate insulin replacement therapy for participants with T1DM
 
Administer anti-hyperglycemic in participants with hyperglycemia
 
	
 
Monitor participants for hyperglycemia or other signs and symptoms of diabetes
 

Hypophysitis	Grade 2	Withhold	
 
Administer corticosteroids and initiate hormonal replacements as clinically indicated
 
	
 
Monitor for signs and symptoms of hypophysitis (including hypopituitarism and adrenal insufficiency)
 

	Grade 3 or 4	Withhold or permanently discontinue a		
Hyperthyroidism	Grade 2	Continue	
 
Treat with non-selective beta-blockers (eg, propranolol) or thionamides as appropriate
 
	
 
Monitor for signs and symptoms of thyroid disorders
 

	Grade 3 or 4	Withhold or Permanently discontinue a		

irAEs	Toxicity Grade (CTCAEv4.0)	Action With Pembrolizumab Monotherapy, Coformulations or IO Combinations	Corticosteroid and/or Other Therapies	Monitoring and Follow-up
Hypothyroidism	Grade 2-4	Continue	
 
Initiate thyroid replacement hormones (eg, levothyroxine or liothyronine) per standard of care
 
	
 
Monitor for signs and symptoms of thyroid disorders
 

Nephritis and renal dysfunction	Grade 2	Withhold	
 
Administer corticosteroids (prednisone 1-2 mg/kg or equivalent) followed by taper
 
	
 
Monitor changes of renal function
 

	Grade 3 or 4	Permanently discontinue		
Myocarditis	Grade 1	Withhold	
 
Based on severity of AE administer corticosteroids
 
	
 
Ensure adequate evaluation to confirm etiology and/or exclude other causes
 

	Grade 2, 3 or 4	Permanently discontinue		
All Other irAEs	Persistent Grade 2	Withhold	
 
Based on severity of AE administer corticosteroids
 
	
 
Ensure adequate evaluation to confirm etiology or exclude other causes
 

	Grade 3	Withhold or discontinue b		
	Recurrent Grade 3 or Grade 4	Permanently discontinue		

AE(s)=adverse event(s); ALT= alanine aminotransferase; AST=aspartate aminotransferase; CTCAE=Common Terminology Criteria for Adverse Events; DRESS=Drug Rash with Eosinophilia and Systemic Symptom; GI=gastrointestinal; IO=immuno-oncology; ir=immune related; IV=intravenous; SJS=Stevens-Johnson Syndrome; T1DM=type 1 diabetes mellitus; TEN=Toxic Epidermal Necrolysis; ULN=upper limit of normal.

**Note: Non-irAE will be managed as appropriate, following clinical practice recommendations.**

a The decision to withhold or permanently discontinue pembrolizumab monotherapy, coformulations or IO combinations is at the discretion of the investigator or treating physician. If control achieved or  $\leq$  Grade 2, pembrolizumab monotherapy, coformulations or IO combinations may be resumed.

b Events that require discontinuation include, but are not limited to: Guillain-Barre Syndrome, encephalitis, myelitis, DRESS, SJS, TEN and other clinically important irAEs (eg, vasculitis and sclerosing cholangitis).

**Dose modification and toxicity management of infusion-reactions related to MK-4280 and pembrolizumab (or MK-4280A)**

Pembrolizumab and MK-4280 (or MK-4280A) may cause severe or life threatening infusion-reactions including severe hypersensitivity or anaphylaxis. Signs and symptoms usually develop during or shortly after drug infusion and generally resolve completely within 24 hours of completion of infusion. Dose modification and toxicity management guidelines on study drug-related infusion reaction are provided in [Table 6](#).

Table 6 Pembrolizumab and MK-4280 (or MK-4280A) Infusion Reaction Dose Modification and Treatment Guidelines

NCI CTCAE Grade	Treatment	Premedication at Subsequent Dosing
Grade 1 Mild reaction; infusion interruption not indicated; intervention not indicated	Increase monitoring of vital signs as medically indicated until the subject is deemed medically stable in the opinion of the investigator.	None
Grade 2 Requires therapy or infusion interruption but responds promptly to symptomatic treatment (e.g., antihistamines, NSAIDs, narcotics, IV fluids); prophylactic medications indicated for $\leq 24$ hrs	Stop Infusion. Additional appropriate medical therapy may include but is not limited to: IV fluids Antihistamines NSAIDs Acetaminophen Narcotics Increase monitoring of vital signs as medically indicated until the subject is deemed medically stable in the opinion of the investigator. If symptoms resolve within 1 hour of stopping drug infusion, the infusion may be restarted at 50% of the original infusion rate (e.g. from 100 mL/hr to 50 mL/hr). Otherwise dosing will be held until symptoms resolve and the subject should be premedicated for the next scheduled dose. Subjects who develop Grade 2 toxicity despite adequate premedication should be permanently discontinued from further study drug treatment	Subject may be premedicated 1.5h ( $\pm 30$ minutes) prior to infusion with: Diphenhydramine 50 mg po (or equivalent dose of antihistamine). Acetaminophen 500-1000 mg po (or equivalent dose of analgesic).

NCI CTCAE Grade	Treatment	Premedication at Subsequent Dosing
Grades 3 or 4 Grade 3: Prolonged (i.e., not rapidly responsive to symptomatic medication and/or brief interruption of infusion); recurrence of symptoms following initial improvement; hospitalization indicated for other clinical sequelae (e.g., renal impairment, pulmonary infiltrates) Grade 4: Life-threatening; pressor or ventilatory support indicated	Stop Infusion. Additional appropriate medical therapy may include but is not limited to: Epinephrine** IV fluids Antihistamines NSAIDs Acetaminophen Narcotics Oxygen Pressors Corticosteroids Increase monitoring of vital signs as medically indicated until the subject is deemed medically stable in the opinion of the investigator. Hospitalization may be indicated. **In cases of anaphylaxis, epinephrine should be used immediately. Subject is permanently discontinued from further study drug treatment.	No subsequent dosing

### 5.2.6.2 Dose Modification and Toxicity Management of AEs Related to mFOLFOX7 or FOLFIRI

#### mFOLFOX7

Dose delays and treatment restarts will be made at the discretion of the site investigator according to institutional guidelines or local standard practice. The recommended dose reduction is stepwise by 20%. Discontinuation of treatment should be considered if dose reduction below the following dosage is required: Oxaliplatin 50 mg/m^2 and 5-FU infusion 1600 mg/m^2 46 to 48 hours.

#### FOLFIRI

Dose delays and treatment restarts will be made at the discretion of the site investigator according to institutional guidelines or local standard practice. The recommended dose reduction is stepwise by 20%. Discontinuation of treatment should be considered if dose reduction below the following dosage is required: Irinotecan 120 mg/m^2 and 5-FU infusion 1600 mg/m^2 46 to 48 hours.

### 5.2.6.3 Dose Modification with Lenvatinib

Lenvatinib dose reduction and interruption for subjects who experience lenvatinib plus pembrolizumab plus MK-4280 combination therapy-related toxicity will be in accordance with the dose modification guidelines described in [Table 7](#). An interruption of study treatment for more than 28 days will require Sponsor approval before treatment can be resumed.

The starting dose of lenvatinib is 20 mg/day. Dose reductions of lenvatinib occur in succession based on the previous dose level (14, 10, 8 mg/day). Any dose reduction below 8 mg/day must be discussed with the Sponsor. Once the lenvatinib dose has been reduced, it may not be increased at a later date, unless the dose has been mistakenly decreased; in this situation, the Sponsor's approval is required to increase the dose.

Refer to the subsections below for management of hypertension (Section 5.2.6.3.1), proteinuria (Section 5.2.6.3.2), diarrhea (Section 5.2.6.3.3), hepatotoxicity (Section 5.2.6.3.4), thromboembolic events (Section 5.2.6.3.5), posterior reversible encephalopathy syndrome/ reversible posterior leukoencephalopathy syndrome (PRES/RPLS; Section 5.2.6.3.6), hypocalcemia (Section 5.2.6.3.7), hemorrhage (Section 5.2.6.3.8), gastrointestinal perforation or fistula formation (Section 5.2.6.3.9), QT prolongation (Section 5.2.6.3.10), and osteonecrosis of the jaw (Section 5.2.6.3.11) as appropriate, before consulting the dose modification table ([Table 7](#)). For overlapping toxicities of pembrolizumab, MK-4280, and lenvatinib, please refer to Section 5.2.6.4.

Table 7 Dose Modification Guidelines for Lenvatinib-Related Adverse Events

Treatment-Related Toxicity a,b	Management	Dose Adjustment
Grade 1 or Tolerable Grade 2		
	Continue treatment	No change
Intolerable Grade 2c,d or Grade 3e,f		
First occurrence	Interrupt lenvatinib until resolved to Grade 0-1, or tolerable Grade 2	Reduce lenvatinib dose to 14 mg once a day (1-level reduction)
Second occurrence (same toxicity or new toxicity)	Interrupt lenvatinib until resolved to Grade 0-1, or tolerable Grade 2	Reduce lenvatinib dose to 10 mg once a day (1-level reduction)
Third occurrence (same toxicity or new toxicity)	Interrupt lenvatinib until resolved to Grade 0-1, or tolerable Grade 2	Reduce lenvatinib dose to 8 mg orally once a day (1-level reduction)
Fourth occurrence (same toxicity or new toxicity)	Interrupt lenvatinib	Discuss with Sponsor
Grade 4g: Discontinue Study Treatment		

Treatment-Related Toxicity a,b	Management	Dose Adjustment

Abbreviations: AE = adverse event; BMI = body mass index; CTCAE = Common Terminology Criteria for Adverse Events.
 
Note: For grading see CTCAE version 4.0. Collect all AE grades (ie, decreasing and increasing CTCAE grade).
 

a. An interruption of study treatment for more than 28 days will require Sponsor approval before treatment can be resumed.

b. Initiate optimal medical management for nausea, vomiting, hypertension, hypothyroidism and/or diarrhea prior to any lenvatinib interruption or dose reduction.

c. Applicable only to Grade 2 toxicities judged by the subject and/or physician to be intolerable.

d. Obese subjects (BMI <math>\geq 30</math>) with weight loss do not need to return to their baseline weight or within 10% of their baseline weight (ie, Grade 1 weight loss). These subjects may restart study intervention at a lower dose once their weight remains stable for at least 1 week and they have a minimum BMI of 25. The new stable weight should be used as the new baseline for further dose reductions.

e. For asymptomatic laboratory abnormalities, such as Grade <math>\geq 3</math> elevations of amylase and lipase that are not considered clinically relevant by the investigator, continuation of treatment should be discussed with Sponsor.

f. For Grade 3 thromboembolic event, permanently discontinue lenvatinib. See Section 5.2.6.3.5.

g. Excluding laboratory abnormalities judged to be non-life-threatening, in which case manage as Grade 3.

		

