#### **2.1.1 Part A**

In Part A, Arm 1 (MK-4280 monotherapy), the study will begin with a 3+3 design to identify a preliminary maximum tolerated dose (MTD) or maximum administered dose (MAD), as described in Section 5.2.1. During 3+3 dose escalation in both arms of Part A, an initial cohort of 3 subjects will be enrolled to a dose level. If none of the 3 subjects experiences a DLT during the first 21 day cycle, escalation to the next dose will occur. If 1 of the 3 subjects experiences a DLT, another 3 subjects will be enrolled at this dose level. If 1 DLT is observed among the 6 subjects, the dose escalation will continue. If more than 1 of 3 or more than 1 of 6 subjects at a dose level develop DLTs, dose escalation will be terminated, and the study will proceed at the previous dose level. At least 2 days of observation will occur between each of the first 3 subjects in the first 2 dose levels.

Treatment in Part A, Arm 2 (MK-4280 in combination with pembrolizumab) will begin with a 3+3 design to identify a preliminary RP2D for Part B. The starting dose of MK-4280 will be at least 1 dose level below that being tested in Part A, Arm 1. A fixed dose of 200 mg pembrolizumab will be used in Part A, Arm 2. During 3+3 dose escalation, at least 2 days of observation will occur between each of the first 3 subjects at the first 2 dose levels. Please note that intrasubject dose escalation is not allowed for any part of this study.

Enrollment to both arms of Part A will occur sequentially. The higher dose level cohort of Part A, Arm 1 must be fully enrolled and all subjects must begin dosing before Part A, Arm 2 is dosed. For example, the 70 mg MK-4280 monotherapy cohort must be fully enrolled and all subjects must have begun dosing before the 21 mg MK-4280 + 200 mg pembrolizumab cohort initiates recruitment and dosing. Doses of MK-4280 in combination with

pembrolizumab will be at least 1 dose level behind the monotherapy dose, and would not exceed the MTD or MAD of Part A, Arm 1. However, once the MTD or MAD for Part A, Arm 1 is established, the dose of MK-4280 in Part A, Arm 2 may continue escalation up to that dose. For enrollment to the last 2 dose levels of Arm 2, all 3 (or 6) subjects in the second highest dose level must complete 1 cycle of treatment and DLT evaluation before the highest dose level may begin enrollment.

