The final number of subjects enrolled in both parts of the study will depend on the DLT observations and, in particular, at what dose the 3+3 design is triggered and what dose is identified as the preliminary RP2D, and on which cohorts (if any) undergo expansion in Part B. For example, in Part A, the maximum sample size across Arm 1 and Arm 2 is 60 subjects (30 subjects each). In Part B, the sample size for the dose confirmation and expansion phase of the study will be a maximum of 516 subjects assuming both the PD-1-treatment-naïve HNSCC and CRC adaptive cohorts are expanded, the gastric cancer cohort (Cohort E) of Arm 1 is opened, and if a de-escalation is needed for the mFOLFOX7, FOLFIRI, and lenvatinib treatment arms. Therefore, the maximum total sample size across Part A and Part B is 576 subjects. See Section 8.9 – Sample Size and Power Calculations for alternate scenarios.

[figure not shown]
The trial will be conducted in conformance with Good Clinical Practices and the MSD Code of Conduct (Appendix 12.1). Adverse events will be evaluated according to criteria outlined in the National Cancer Institute (NCI) Common Terminology Criteria for Adverse Experiences (CTCAE), Version 4 (Appendix 12.5).

Specific procedures to be performed during the trial, as well as their prescribed times and associated visit windows, are outlined in the Trial Flow Chart - Section 6.0. Details of each procedure are provided in Section 7.0 – Trial Procedures.

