#### **4.2.2.1.6 Rationale for Lenvatinib Dose**

The dosing regimen of lenvatinib was selected based on the results of the Phase 1b portion of KEYNOTE-146, which determined the MTD and RP2D as lenvatinib 20 mg QD when administered in combination with pembrolizumab 200 mg Q3W [43].

If the TPI design calls for a de-escalation, reduced doses of lenvatinib (14 mg and 10 mg) will be used. If the TPI design calls for additional de-escalation, enrollment into Arm 6 will be closed.

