MK-4280A	800 mg MK-4280 + 200 mg pembrolizumab	Q3W	IV infusion	Day 1 of each 21-day cycle	Test Product

Drug	Dose/ Potency	Dose Fre- quency	Route of Administration	Regimen/ Treatment Period	Use
Part B, Arm 6					
MK-4280	800 mg	Q3W	IV infusion	Day 1 of each 21-day cycle	Test Product
Pembrolizumab	200 mg	Q3W	IV Infusion	Day 1 of each 21-day cycle	Test Product
Lenvatinib	20 mg 14 mg 10 mg 8 mg	QD	Oral	QD of each 21-day cycle	Test Product

a. From a preliminary analysis of MK-4280 PK and pharmacodynamic biomarker data collected during Part A, the preliminary RP2D for MK-4280 to carry forward into Part B of the study was determined to be 200 mg. Following the accumulation of more data, the Sponsor has elected to test the higher 800 mg dose of MK-4280 in Part B as well.
 
b. Reduced doses for components of mFOLFOX7 and/or FOLFIRI will only be used if the TPI calls for a de-escalation.
 
c. Depending on local practice guidelines, levofolinate calcium (200 mg/m^2 Q2W) may be substituted for leucovorin.
 
d. Every attempt should be made to source these supplies from a single lot/batch number. The trial site is responsible for recording the lot number, manufacturer, and expiry date for any locally purchased product as per local guidelines unless otherwise instructed by the Sponsor.
					

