### **5.2.2.5 Arm 6 – MK-4280 + Pembrolizumab + Lenvatinib**

Subjects with CRC that have received 2 lines of prior systemic therapy in Part B (Cohort G) will be assigned to receive MK-4280 800 mg Q3W in combination with pembrolizumab 200 mg Q3W and lenvatinib 20 mg QD. A TPI design will be used to assess the safety and tolerability of Arm 6 in the first 14 subjects enrolled. If the TPI calls for a de-escalation, reduced doses of lenvatinib (14 mg and 10 mg) will be used. The doses of MK-4280 and pembrolizumab will not be adjusted.

Trial treatment for all arms should begin on the day of treatment allocation/randomization or as close as possible to the date on which the subject is allocated/assigned.

The investigator shall take responsibility for and shall take all steps to maintain appropriate records and ensure appropriate supply, storage, handling, distribution and usage of trial treatments in accordance with the protocol and any applicable laws and regulations.

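### Table 7's fixed lenvatinib doses (14, 10, 8 mg) fit only a 20 mg start; from a planned 14 mg or 10 mg start the first step is no reduction or an increase

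*Combined protocol and SAP*

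**What the plan says.** Section 5.2.6.3 makes Table 7 the rule for lenvatinib interruption and reduction. Above the table it says: "The starting dose of lenvatinib is 20 mg/day. Dose reductions of lenvatinib occur in succession based on the previous dose level", with the steps 14, 10 and 8 mg/day in brackets. It adds: "Any dose reduction below 8 mg/day must be discussed with the Sponsor".

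For an intolerable Grade 2 or a Grade 3 event, Table 7 interrupts lenvatinib until recovery and then sets a dose by occurrence number. The first row is "Reduce lenvatinib dose to 14 mg once a day (1-level reduction". The second and third rows give 10 mg and 8 mg with the same one-level label. The fourth refers the site to the Sponsor. Footnotes a to g give no other set of doses.

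Other sections plan lower starts in Arm 6:

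- Section 4.2.2.1.6: "If the TPI design calls for a de-escalation, reduced doses of lenvatinib (14 mg and 10 mg) will be used".
- Section 5.2.2.5: "If the TPI calls for a de-escalation, reduced doses of lenvatinib (14 mg and 10 mg) will be used".
- Section 5.2.3.5 enrols new subjects at each new dose and lets a reduced dose become the RP2D for the rest of Cohort G.
- Section 2.1.2 sets the Part B maximum of 516 on several assumptions, including "if a de-escalation is needed for the mFOLFOX7, FOLFIRI, and lenvatinib treatment arms".
- Table 3 lists the Arm 6 doses as "20 mg 14 mg 10 mg 8 mg".

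**The concern.** The table uses the occurrence number as a stand-in for the dose level. The two agree only when the subject's first dose was 20 mg. For a subject who starts at 14 mg or 10 mg because the TPI has de-escalated, the milligram value in a cell and the one-level label in the same cell give different instructions.

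The conflict appears only after a higher lenvatinib dose has been judged too toxic, and it governs management of an intolerable Grade 2 or a Grade 3 event. A site that follows the milligram value would leave a 14 mg subject unreduced after a first event. Two sites could dose the same event differently.

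**Working it through.** **Inputs.** Dose ladder 20, 14, 10, 8 mg (Table 3; Section 5.2.6.3). Table 7 doses 14, 10, 8 mg for occurrences 1, 2, 3. Possible starting doses 20, 14 and 10 mg (Sections 4.2.2.1.6, 5.2.2.5, 5.2.3.5).

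**Table as written.** Change from start = tabulated dose - starting dose. The last column steps one ladder level down from the current dose.

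| Start (mg) | 1st | 2nd | 3rd | Rows not below start | One-level rule gives |
|---|---|---|---|---|---|
| 20 | 14 - 20 = -6 | 10 - 20 = -10 | 8 - 20 = -12 | 0 of 3 | 14, 10, 8, then Sponsor |
| 14 | 14 - 14 = 0 | 10 - 14 = -4 | 8 - 14 = -6 | 1 of 3 | 10, 8, then Sponsor |
| 10 | 14 - 10 = +4 | 10 - 10 = 0 | 8 - 10 = -2 | 2 of 3 | 8, then Sponsor |

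The table reproduces the one-level rule exactly from 20 mg and from no other start. The tabulated dose first falls below the start at the 1st, 2nd and 3rd occurrence for starts of 20, 14 and 10 mg. Under the one-level rule it does so at the 1st occurrence every time. First-event change, table against rule: from 14 mg, 0 against 10 - 14 = -4 mg; from 10 mg, +4 against 8 - 10 = -2 mg.

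**Is the branch planned?** Part B cohort maxima from Section 2.1.2:

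- A: 20 + 100 + 40 + 40 = 200
- B: 20 + 20 = 40
- C: 40
- D: 20
- E: 80 + 20 = 100
- F: 20
- G: 40

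The sum is 460. The stated maximum is 516, and 516 - 460 = 56 = 4 x 14. That fits one extra 14-subject group each for Arms 3 and 4 and two for Arm 6 (14 mg and 10 mg). The documents do not itemise the 56, so this split is an inference.

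**How likely is a reduced start?** The documents give no DLT rate for the triplet, so the rates below are assumptions. Section 5.2.3.3, applied to Arm 6 by Section 5.2.3.5, allows the next lower dose to be expanded if more than 5 of 14 subjects have a DLT. The first calculation is P(X >= 6), X ~ Binomial(14, p). The second also applies the de-escalate and unacceptably-toxic cells of Table 4 at earlier looks. It assumes looks at 9 and 14 subjects if the first 3 have no DLT, and otherwise at 6, 9, 12 and 14. The limits are 3, 4, 6 and 6 DLTs at 6, 9, 12 and 14 subjects.

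| Assumed true DLT rate at 20 mg | 14-subject rule only | With earlier looks |
|---|---|---|
| 10% | 0.1% | 2% |
| 20% | 4% | 14% |
| 30% | 22% | 37% |
| 40% | 51% | 65% |

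A 10 mg start needs two successive steps. Treating the dose levels as independent and using the earlier-look figures:

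- 20% at both levels: 0.136 x 0.136 = 2%
- 30% then 20%: 0.373 x 0.136 = 5%
- 30% at both levels: 0.373 x 0.373 = 14%

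**The case against.** The strongest reply is that the protocol already supplies the right rule.

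- The sentence above the table steps down from the previous dose.
- Each disputed cell calls itself a one-level reduction, which neither 14 to 14 mg nor 10 to 14 mg is.
- Section 5.2.6.3.1, which sites consult before Table 7 for hypertension, words its reductions relative to the current level.
- Section 5.2.6 bars re-escalation after a toxicity reduction and allows departures from the tables after consulting the Sponsor.
- Section 2.1.1 adds that "intrasubject dose escalation is not allowed for any part of this study".

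Read together, these give 14 to 10 to 8 mg, or 10 to 8 mg. A site is unlikely to raise a dose under a cell that says to reduce it.

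Much of this stands. The intent is clear enough to infer, and 10 to 14 mg cannot be meant. The 10 mg start is also the less likely branch. The DLT probabilities describe the TPI trigger, not misdosing, and 6 DLTs in 14 permits rather than compels de-escalation.

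The reply does not correct the table. The ban on escalation leaves staying at 14 mg open for a subject who started there, and that is the more likely reduced start. The section directs sites to Table 7, where the explicit milligram values contradict the label in the same cells.

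**Conclusion.** The concern holds and is minor. Table 7 is wrong as written for one of three rows from a 14 mg start and two of three from a 10 mg start. It is correct for every row from 20 mg. The first-event dose exceeds the one-level dose by 4 mg from a 14 mg start (14 against 10) and by 6 mg from a 10 mg start (14 against 8).

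These figures rest only on the stated ladder and table. The chance of reaching a reduced start depends on assumed DLT rates: 4% to 51% for true rates of 20% to 40% under the 14-subject rule, and close to zero at 10%.

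Harm is limited because lenvatinib is interrupted until recovery in the same rows and the intended rule can be inferred. DLTs are counted in Cycle 1 (Section 5.2.4), so the TPI and RP2D decision is largely unaffected.

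**What to change.** Reword the first three reduction rows of Table 7 as a reduction of one dose level from the subject's current dose on the ladder 20, 14, 10, 8 mg. In Section 5.2.6.3, describe 20 mg as the initial cohort dose rather than the only starting dose.

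As a tidy-up, let the row that refers the site to the Sponsor apply whenever the next step would fall below 8 mg, whatever the occurrence number. The existing rule on doses below 8 mg already requires this.

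The three reduction steps from a 20 mg start are unchanged. The cost is rewording one table and one sentence in the next amendment, with no added subjects, visits or procedures.
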